9.5.3 Patient's Global Assessment of Disease Activity Visual Analog Scale (VAS)

The subject will assess his/her disease activity for the past 24 hours using a Patient's Global Assessment of Disease VAS. The range is 0 to 100 mm with no activity being indicated by 0 and severe activity by 100.

9.5.4 Physician's Global Assessment of Disease Activity Visual Analog Scale (VAS)

The physician will assess Patient's disease activity at the time of visit using a Physician's Global Assessment of Disease VAS. The range is 0 to 100 mm with no activity being indicated by 0 and severe activity by 100.

9.5.5 Patient's Global Assessment of Pain

The subject will assess his/her pain in the previous week using a Patient's Global Assessment Pain VAS. The range is 0 to 100 mm with no pain being indicated by 0 and severe pain by 100.

9.5.6 Disability Index of Health Assessment Questionnaire (HAQ-DI)

HAQ-DI is a self-reported patient outcome measurement. It is calculated as the mean of the scores from 8 following categories with a range 0 – 3: Dressing and Grooming, Rising, Eating, Walking, Hygiene, Reach, Grip, and Activities. The higher the score is, the more likely to associate with morbidity and mortality for the RA patient.

The maximum score for all the questions in each category is considered as the score for the category. The Standard disability index (HAQ-DI) takes into account the subject's use of aids or devices or assistance in the scoring algorithm for a disability category. For each of the eight disability categories there is an AIDS OR DEVICES companion variable(s) that is used to record the type of assistance, if any, a subject uses for his/her usual activities. If aids or devices and/or assistance from another person are checked for a disability category, the score for this category is set to 2 (much difficulty), if the original

score is 0 (no difficulty) or 1 (some difficulty). The HAQ-DI is then calculated by summing the adjusted categories scores and dividing by the number of categories answered. The HAQ-DI cannot be calculated if the patient does not have scores for at least 6 categories.

9.5.7 Disease Activity Score (DAS28)

DAS28(CRP) and DAS28(ESR) are composite indices to assess disease activity in RA patients using hsCRP or ESR measurement respectively. The DAS provides a score between 0 and 10, indicating how active the rheumatoid arthritis is at the time of measurement.

DAS28(CRP) and DAS28(ESR) can be calculated based on Tender Joint Count, Swollen Joint Count, Patient's Global Assessment of Disease Activity (PtGA) (in mm), and hsCRP (in mg/L) or ESR (in mm/hr).

$$\text{DAS28 (CRP)} = 0.56 \times \sqrt{\text{TJC28}^*} + 0.28 \times \sqrt{\text{SJC28}^{**}} + 0.36 \times \ln(\text{hsCRP}^{\&} + 1) + 0.014 \times \text{PtGA}^{\gg} + 0.96$$

$$\text{DAS28 (ESR)} = 0.56 \times \sqrt{\text{TJC28}^*} + 0.28 \times \sqrt{\text{SJC28}^{**}} + 0.70 \times \ln(\text{ESR}^{\#}) + 0.014 \times \text{PtGA}^{\gg}$$

* TJC28 refers to the Subject's total Tender Joint Count out of the provided 28 evaluated joints.

** SJC28 refers to the Subject's total Swollen Joint Count out of the provided 28 evaluated joints.

& hsCRP refers to the high-sensitivity c-reactive protein lab value. hsCRP unit in the DAS28 (CRP) equation is expressed as mg/L.

ESR refers to the Erythrocyte sedimentation rate. ESR unit in the DAS28 (ESR) equation is expressed as mm/hr.

» PtGA refers to the Patient's Global Assessment of Disease Activity.

Where $\sqrt{\quad}$ is square root and \ln is natural log.

Table 9. Anatomical Joints for DAS28(CRP) Calculation

Shoulder	Elbow	Wrist	Thumb Interphalangeal
Metacarpophalangeal I	Metacarpophalangeal II	Metacarpophalangeal III	Metacarpophalangeal IV
Metacarpophalangeal V	Proximal Interphalangeal II	Proximal Interphalangeal III	Proximal Interphalangeal IV
Proximal Interphalangeal V	Knee		

To calculate observed DAS28 scores, the observed component value will be calculated first. Then the components will be included in the calculation per the DAS formula selected. If any observed component is missing in a window, then the observed DAS28 score will be missing.

9.5.8 Simplified Disease Activity Index (SDAI)

SDAI is a composite continuous index to assess disease activity based on TJC28, SJC28, Patient's Global Assessment of Disease Activity (PtGA) (in cm, 0 – 10), Physician's Global Assessment of Disease Activity (PhGA) (in cm, 0 – 10) and hsCRP (mg/dL). It can be derived as follows:

$$\text{SDAI} = \text{TJC28} + \text{SJC28} + \text{PtGA (cm)} + \text{PhGA (cm)} + \text{hsCRP (mg/dL)}.$$

To calculate observed SDAI scores, the observed component value will be calculated first. Then the components will be included in the calculation per the SDAI formula selected. If any observed component is missing in a window, then the observed SDAI score will be missing.

9.5.9 Clinical Disease Activity Index (CDAI)

CDAI is a composite continuous index to assess disease activity without using hsCRP measurement. It can be calculated based on TJC28, SJC28, Patient's Global Assessment of Disease Activity (PtGA) (in cm, 0 – 10) and Physician's Global Assessment of Disease Activity (PhGA) (in cm, 0 – 10). It can be derived as follows:

$$\text{CDAI} = \text{TJC28} + \text{SJC28} + \text{PtGA (cm)} + \text{PhGA (cm)}.$$

To calculate observed CDAI scores, the observed component value will be calculated first. Then the components will be included in the calculation per the CDAI formula selected. If any observed component is missing in a window, then the observed CDAI score will be missing.

9.5.10 Clinical Remission (CR) and Low Disease Activity (LDA)

Clinical remission (CR) and low disease activity (LDA) based on DAS28 (CRP), DAS28(ESR), SDAI and CDAI are defined as follows:

	DAS28 (CRP) and DAS28 (ESR)	SDAI	CDAI
LDA	≤ 3.2	≤ 11.0	≤ 10
CR	< 2.6	≤ 3.3	≤ 2.8

9.5.11 ACR/EULAR Boolean Remission

ACR/EULAR Boolean remission is defined based on the following four criteria:

- Tender joint count ≤ 1 (based on 28 joints)
- Swollen joint count ≤ 1 (based on 28 joints)
- CRP ≤ 1 mg/dL
- Patient global assessment of disease activity ≤ 10 (mm)

All four criteria must be satisfied at a visit for a subject to be classified as achieving ACR/EULAR Boolean remission.

9.5.12 Modified Total Sharp Score (mTSS)

The radiographic outcome will be assessed and scored according to Sharp's method (Van der Heijde modification) centrally by two qualified physicians/radiologists who will be blinded to the site number, subject number, treatment allocation, time sequence and clinical response.

Calculation of the Modified Total Sharp Score

To obtain the total mTSS score, scores for joint erosions and JSN in both the hands and feet will be added together.

The range of scores is summarized below.

	Hands	Feet	Total (Hands and Feet)
Joint Erosion Score Range	0 – 160	0 – 120	0 – 280
Joint Space Narrowing Range	0 – 120	0 – 48	0 – 168
mTSS Range for Joint Erosion and JSN	0 – 280	0 – 168	0 – 448

The following joints will be examined for assessing Joint Erosions:

Foot^a		Hand^b	
1 st IP	1 st IP	4 th PIP	Navicular
1 st MTP	1 st MCP	4 th MCP	Lunate
2 nd MTP	2 nd PIP	5 th PIP	Radius
3 rd MTP	2 nd MCP	5 th MCP	Ulnar
4 th MTP	3 rd PIP	1 st MC	
5 th MTP	3 rd MCP	Multangular ^c	

a. IP: Inter-Phalangeal, MTP: Metatarso-Phalangeal.

b. IP: Inter-Phalangeal, PIP: Proximal Inter-Phalangeal, MCP: Metacarpophalangeal, MC: Metacarpal.

c. Trapezium/Trapezoid as read as one unit-Multangular.

The following joints will be examined for assessing Joint Space Narrowing:

Foot^a		Hand^b	
1 st IP	1 st MCP	4 th MCP	MN
1 st MTP	2 nd PIP	5 th PIP	CNL
2 nd MTP	2 nd MCP	5 th MCP	RC
3 rd MTP	3 rd PIP	3 rd CMC	
4 th MTP	3 rd MCP	4 th CMC	
5 th MTP	4 th PIP	5 th CMC	

a. IP: Inter-Phalangeal, MTP: Metatarso-Phalangeal.

b. PIP: Proximal Inter-Phalangeal, MCP: Metacarpo-Phalangeal, CMC: Carpo-Metcarpal, MN: Multangular-Navicular, CNL: Capitate-Navicular Lunate, RC: Radio-Carpal.

For each Joint and Bone assessed, scores range as follows:

- Joint Erosions: 0 – 5 (hands/wrists) or 0 – 10 (feet) to characterize the extent of erosions (where 0 denotes no erosion).
- Joint Space Narrowing: 0 – 4 to characterize the extent of Joint Space Narrowing (JSN) (where 0 denotes no narrowing).

Joint Erosion and JSN scores for each reader are calculated by taking the sum of the left and right joints as shown below.

$$\text{Erosion}_{\text{Reader } i} = \text{Erosion}_{\text{Left}} + \text{Erosion}_{\text{Right}}$$

$$\text{JSN}_{\text{Reader } i} = \text{JSN}_{\text{Left}} + \text{JSN}_{\text{Right}} \text{ for } i = 1, 2.$$

Thus, the maximum joint erosion score for all 32 joints in hands/wrists is 160. The maximum joint erosion score for all 12 joints in feet is 120. Thus, the total joint erosion score for hands/wrists and feet is 280.

The maximum score for JSN in all 30 hand/wrist joints is 120. The maximum score for JSN in all 12 feet joints is 48. Thus, the total JSN score for hand/wrist and feet is 168.

Since two independent readers evaluate each film, the mean score will be calculated for the two readers from the individual joint erosion and JSN scores as shown below:

$$\text{Joint Erosion} = \frac{\text{Erosion}_{\text{Reader1}} + \text{Erosion}_{\text{Reader2}}}{2}$$

$$\text{JSN} = \frac{\text{JSN}_{\text{Reader1}} + \text{JSN}_{\text{Reader2}}}{2}$$

The mTSS for each reader is defined as the sum of the joint erosion and JSN scores:

$$\text{TSS}_{\text{Reader } i} = \text{JointErosion}_{\text{Reader } i} + \text{JSN}_{\text{Reader } i} \text{ for } i = 1, 2.$$

The average modified TSS from the two readers will be used for all x-ray endpoint calculations.

$$\text{TSS} = \frac{\text{TSS}_{\text{Reader1}} + \text{TSS}_{\text{Reader2}}}{2}$$

Sensitivity analysis may be performed as needed.

Adjudication Process

Two reviewers will independently review the images. Adjudication will occur for all subjects with a discrepancy [REDACTED] between the two reviewers' mTSS change scores, in which case another reviewer, different from the reviewers who performed primary assessments, will make a third, independent assessment.

For the calculation of mTSS, the score of two closest reads (out of the two primary reviewers and the adjudicator) will be used. In the case of equal distance, the average of the three reads will be used.

9.5.13 EuroQoL-5D (EQ-5D-5L)

EQ-5D is a standardized measure of health status developed by the EuroQol Group in order to provide a simple, generic measure of health for clinical and economic appraisal. The EQ-5D consists of 2 pages. The first page measures 5 dimensions of the health status (mobility, self-care, usual activities, pain/discomfort, and anxiety/depression) with 5 levels per dimension (no problems, slight problems, moderate problems, severe problems, and extreme problems corresponding to Level 1 to Level 5 respectively). The second page is an EQ Visual Analogue Scale (EQ VAS). EQ-5D health states, defined by the EQ-5D-5L descriptive system on the first page, may be converted into a single index value. The change from baseline of the index value and EQ VAS will be analyzed and reported. UK scoring algorithm will be used.

9.5.14 Form SF-36v2

The 36-Item Short Form, Version 2 (SF-36v2) Questionnaire with 4 week recall will be completed by the subject at Baseline, Weeks 4, 8 and at study completion (Week 12 or at PD). The SF-36v2 health survey consists of 36 general health questions and this study is

using the form for 4 weeks recall period (standard form). It has 2 components: physical and mental. For each component, a transformed summary score is calculated using 8 sub-domains: physical functioning, role-physical, bodily pain, general health, vitality, social functioning, role-emotional, and mental health.

The coding and scoring for the SF-36 will use the software provided by QualityMetrics.

9.5.15 Functional Assessment of Chronic Illness Therapy-Fatigue (FACIT-F)

Fatigue is one of the most frequent complaints of the elderly and is strongly associated with loss of independence and decreased physical activity and functional decline. One validated tool to measure fatigue is FACIT Fatigue Scale v4. The FACIT Fatigue Scale is a short, 13-item, easy to administer tool that measures an individual's level of fatigue during their usual daily activities over the past week. Each of the fatigue and impact of fatigue items are measured on a four point Likert scale (4 = not at all to 0 = very much). The FACIT Fatigue Scale is ranged from 0 to 52 and the higher the score, the better the quality of life.

Score for each item is calculated by either subtracted from 4 or adding 0 depending on whether it is a reversal item or not. FACIT Fatigue Scale is then calculated by adding up all item scores, multiplied by 13 and divided by the number of items answered. It is essentially a prorated subscale if there are missing values for some items. If less than or equal to 50% of the items are answered (e.g., 6 out of 13), the proration is not acceptable and the scale will not be computed.

9.5.16 Work Instability Scale for Rheumatoid Arthritis (RA-WIS)

The 23-item RA-WIS is a simple validated tool to evaluate work instability (the consequence of a mismatch between an individual's functional ability and their work tasks). It can be self-administered by the patients. To calculate the RA-WIS scale, one can simply add up the number of "true" responses. If the scale is < 10, it means low risk and no action is needed. If the scale is between 10 and 17, it means medium risk and

appropriate advice and information should be given. If the scale is > 17 , it means high risk and it could warrant referral.

10.0 Safety Analysis

10.1 General Considerations

Safety analyses will be carried out using the Safety Analysis Set. There are three sets of planned safety analysis: safety analysis up to Week 14, safety analysis up to Week 26 censored at treatment switching, and long-term safety analysis. Missing safety data will not be imputed.

10.1.1 Safety Analysis up to Week 14

Standard safety analysis by the "as treated" treatment groups of placebo, ADA 40 mg EOW, Upadacitinib 15 mg QD groups will be performed on safety data up to Week 14. No protocol-defined treatment switching will occur prior to this time point.

The standard safety analyses will include reporting of adverse events (AEs), laboratory, and vital signs measurements. Frequency tables of subjects with treatment-emergent adverse events (TEAEs) by system organ class (SOC) and by preferred term (PT) as in the Medical Dictionary for Regulatory Activities (MedDRA) dictionary will be provided by treatment group. Mean changes from baseline in all continuous laboratory parameters and vital signs variables at each visit will be summarized by "as treated" treatment group. Frequency tables of subjects meeting criteria for potentially clinically significant vital sign values and for potentially clinically significant laboratory values will be provided by treatment group.

10.1.2 Safety Analysis up to Week 26 Censored at Treatment Switching

Standard safety analysis by the "as treated" treatment groups of placebo, ADA 40 mg EOW, Upadacitinib 15 mg QD groups will be performed on safety data up to Week 26.

For subjects who are rescued to a different study drug prior to Week 26, safety data will be censored at the time of treatment switching.

The standard safety analyses will include reporting of adverse events (AEs), laboratory, and vital signs measurements. Frequency tables of subjects with treatment-emergent adverse events (TEAEs) by system organ class (SOC) and by preferred term (PT) as in the Medical Dictionary for Regulatory Activities (MedDRA) dictionary will be provided by treatment group. Mean changes from baseline in all continuous laboratory parameters and vital signs variables at each visit will be summarized by "as treated" treatment group. Frequency tables of subjects meeting criteria for potentially clinically significant vital sign values and for potentially clinically significant laboratory values will be provided by treatment group.

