### **Discontinuation of Study Drug and Continuation of Study Participation (Period 1 and Period 2)**

Subjects may discontinue study drug treatment, but may choose to continue to participate in the study (refer to Section 5.4.1 for additional details). Subjects who prematurely discontinue study drug should complete a Premature Discontinuation Visit (PD visit) as soon as possible, preferably within 2 weeks. Afterwards, subjects should follow the regular visit schedule as outlined in Table 2 and Table 4, and adhere to all study procedures except for dispensing study drug, PK sample collection, and blood sample collection for optional exploratory research and validation studies. In addition, all future rescue and efficacy-driven discontinuation criteria no longer apply; this includes 20% TJC/SJC calculations at Weeks 14 – 22, and Week 48 and thereafter, as well as CDAI calculation at Week 26, if applicable. If at any point a subject no longer wants to provide assessments (withdrawal of informed consent) following discontinuation of study drug, a second PD visit is not required.

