### **6.1.7 Toxicity Management**

The toxicity management of the AEs including AEs of special interest consists of safety monitoring (review of AEs on an ongoing basis, and periodical/ad hoc review of safety issues by a safety data monitoring committee), interruption of study drug dosing with appropriate clinical management if applicable, and discontinuation of the subjects from study drug. The management of specific AEs and laboratory parameters is described below.

For subjects who discontinued study drug but continued study participation and are instead on standard of care therapies, these toxicity management requirements do not apply (including alerts from the central lab) and any intolerability to standard of care therapies should be managed by the prescribing physician.

**Serious Infections:** Subjects should be closely monitored for the development of signs and symptoms of infection during and after treatment with study drug. Study drug should be interrupted if a subject develops a serious infection or an opportunistic infection. A subject who develops a new infection during treatment with study drug should undergo prompt diagnostic testing appropriate for an immunocompromised subject. As appropriate, antimicrobial therapy should be initiated, and the subject should be closely monitored. Re-challenge with study drug may occur once the infection has been successfully treated. If study drug has been interrupted for a serious infection for more than 14 consecutive days during the first 26 weeks, more than 21 days between Weeks 26 and 48 or more than 30 consecutive days thereafter, the subject must be discontinued from study drug. Subjects who develop active TB must be permanently discontinued from study drug.

**Gastrointestinal Perforation:** Subjects presenting with the onset of signs or symptoms of a serious gastrointestinal event should be evaluated promptly for early identification of

gastrointestinal perforation. If the diagnosis of gastrointestinal perforation is confirmed, the subject must be discontinued from study drug.

**Cardiovascular Events:** Subjects presenting with potential cardiovascular events should be carefully monitored. These events will be reviewed and adjudicated by an independent Cardiovascular Adjudication Committee in a blinded manner.

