5.0 Analysis Populations and Analysis Windows

5.1 Analysis Populations

Full Analysis Set (FAS)

The Full Analysis Set (FAS) includes all randomized subjects who received at least one dose of study drug. The FAS will be used for all efficacy and baseline analyses.

Per Protocol Analysis Set

The Per Protocol Analysis Set represents a subset of the FAS and consists of all FAS subjects who did not meet any major protocol deviations up to Week 12 in Period 1 of the

study. Additional analysis of the primary efficacy endpoint will be conducted on the Per Protocol analysis set, in order to evaluate the impact of major protocol deviations.

Major protocol deviations (ICH deviations and other clinically significant non-ICH deviations) will be identified prior to data base lock.

Safety Analysis Set

The Safety Analysis Set consists of all subjects who received at least one dose of study drug. For the Safety Analysis Set, subjects are assigned to a treatment group based on the "as treated" treatment group, regardless of the treatment randomized. The "as treated" is determined by the treatment the subject received during the majority of the subject's drug exposure time in the analysis period.

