10.2 Analysis of Adverse Events

A treatment-emergent Adverse Event (TEAE) is defined as an adverse event with an onset date that is after the first dose of study drug, and no more than 30 days or 5 half-lives of the drug, whichever is larger, after the last dose of study drug. Specifically, 30 days will be used for Upadacitinib and placebo, and 70 days will be used for ADA.

Events where the onset date is the same as the study drug start date are assumed to be treatment-emergent, unless the study drug start time and the adverse event start time are collected and the adverse event start time is prior to the study drug start time. If an incomplete onset date was collected for an adverse event, the event will be assumed to be treatment-emergent unless there is other evidence that confirms that the event was not treatment-emergent (e.g., the event end date was prior to the study drug start date).

Adverse event data will be presented by SOC and PTs using MedDRA version 19.0 or most up to date version. All adverse event tables will be sorted in alphabetical order by SOC and PT and descending percentages for each treatment group.

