10.3.2.1 Assessment of Mean Change from Baseline in Clinical Laboratory Variables

Analyses of mean change from baseline in continuous hematology, chemistry, and urinalysis variables which are measured longitudinally will be performed by visits and by "as treated" treatment group. For each change from baseline analysis, the following summary statistics will be presented for each treatment group: sample size, baseline mean, visit mean, and the mean, standard deviation, and median of the changes from baseline.

In addition, similar analyses will be conducted for percentage change from baseline in hemoglobin, LDL-C, HDL-C and triglycerides.

Analysis of mean change and mean percent change by visit will only be provided for "safety analysis up to Week 26 censored at treatment switching." Analysis will not be repeated for "safety analysis up to Week 14," because it will be a subset of the former.

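### Short-term lab and vital-sign summaries, and the long-term by-visit mean changes, have no limit relative to last dose, so off-drug values are reported under the drug the subject left

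*SAP*

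**What the plan says.** SAP 10.1.2 defines the Week 26 safety set by as-treated group and covers all three data types: "The standard safety analyses will include reporting of adverse events (AEs), laboratory, and vital signs measurements". Its one censoring rule is "For subjects who are rescued to a different study drug prior to Week 26, safety data will be censored at the time of treatment switching". SAP 10.1.1 (to Week 14) has no censoring rule, since no switch is planned before then.

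The lab and vital-sign sections (SAP 10.3.2 and 10.4.2) refer back to these sets and add no limit. On mean changes, SAP 10.3.2.1 says: "Analyses of mean change from baseline in continuous hematology, chemistry, and urinalysis variables which are measured longitudinally will be performed by visits". The visit windows in SAP Table 1 depend only on days since first dose. Group membership is "determined by the treatment the subject received during the majority of the subject's drug exposure time in the analysis period" (SAP 5.1), so it does not end when dosing ends.

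Adverse events are handled differently. SAP 10.2 ends the treatment-emergent period a fixed time after last dose: "Specifically, 30 days will be used for Upadacitinib and placebo, and 70 days will be used for ADA". SAP 10.2.1.1 and 10.2.1.2 repeat the overview and the tables by system organ class and preferred term without that limit, by randomized group, as a sensitivity analysis.

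Protocol 5.1 has subjects who stop study drug but stay in the study keep attending at the planned times. They are to "adhere to all study procedures except for dispensing study drug, PK sample collection, and blood sample collection for optional exploratory research and validation studies". Protocol 6.1.7 recognises that such subjects may be receiving other treatment: "For subjects who discontinued study drug but continued study participation and are instead on standard of care therapies, these toxicity management requirements do not apply".

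**The concern.** A subject who stops study drug without switching cannot meet the only censoring event before Week 26, because Protocol 5.1 also says that the rescue criteria cease to apply once drug is stopped. That subject's later labs and vital signs stay in the as-treated group to Week 26. In the treatment-sequence mean changes they stay beyond that, since SAP 7.0 allows for subjects who enter Period 2 having stopped drug in Period 1.

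Two effects follow. Values that have drifted back towards baseline dilute the by-visit mean change, and an off-drug value can become the final value in the shift table. Values made abnormal by later therapy can add cases to the potentially clinically significant (PCS) and liver tables. Period 1 objective 3 is the between-group comparison of safety, and the main lab tables would cover a longer risk period than the main adverse event tables.

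The rule is also uneven. An upadacitinib subject rescued to study adalimumab is censored. One who stops and starts commercial adalimumab, a case that Protocol 5.1 foresees, is not.

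**Working it through.** The plan states no figure on this point, so there is none to reproduce. The check has four steps.

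**1. Is there a last-dose limit anywhere?** For labs and vital signs, none appears in SAP 5.1, 5.2, 10.1.1, 10.1.2, 10.3.2 or 10.4.2, or in Protocol 8.1.5. There is also none for the mean changes by treatment sequence in SAP 10.3.3.1 and 10.4.3. The long-term PCS and liver summaries (SAP 10.3.3.2, 10.3.3.3 and the PCS part of 10.4.3) are tied to the treatment received at the time of the event. Elsewhere the SAP does state such limits: 30/70 days for adverse events, and removal of values after drug discontinuation in the Observed Cases rule (SAP 9.1.2).

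**2. Which values are affected?** Inputs are the target days in SAP Table 1 and the limits in SAP 10.2. Days off drug = visit day − last-dose day. Example with last dose at Week 4 (Day 29):

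| Visit | Day | Days off drug | Over 30 | Over 70 |
|---|---|---|---|---|
| Week 8 | 57 | 28 | no | no |
| Week 12 | 85 | 56 | yes | no |
| Week 14 | 99 | 70 | yes | no |
| Week 18 | 127 | 98 | yes | yes |
| Week 22 | 155 | 126 | yes | yes |
| Week 26 | 183 | 154 | yes | yes |

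All six visits enter the tables. Five of six lie beyond the upadacitinib/placebo limit and three of six beyond the adalimumab limit. A late stop matters less: with last dose at Week 18 (Day 127), Weeks 22 and 26 are 28 and 56 days off drug, so one of two exceeds 30 days and none exceeds 70. In general the Week 26 value lies beyond the limit when the last dose is before Day 183 − 30 = 153 (upadacitinib, placebo) or before Day 183 − 70 = 113 (adalimumab).

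**3. How much dilution?** Let m be the on-drug mean change, f the share of assessed subjects who are off drug, and r the fraction of the change that has reversed. If off-drug subjects would otherwise have shown the average change, the reported mean is m × (1 − f × r). The documents give neither f nor r. The nearest figure is the 10% dropout allowance in Protocol 8.2 and SAP 4.3.

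- f = 0.02, r = 1: 98% of m
- f = 0.05, r = 1: 95% of m
- f = 0.10, r = 1: 90% of m
- f = 0.10, r = 0.5: 1 − 0.10 × 0.5 = 95% of m

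At f = 0.10 that is 600 × 0.10 = 60 upadacitinib subjects and 300 × 0.10 = 30 adalimumab subjects, if all of them keep attending.

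**4. Direction by table.** By-visit means are diluted when values recover. The final category can be replaced outright by an off-drug value. PCS and liver tables count subjects who meet a criterion, and the maximum-category shift takes the worst grade, so off-drug values can only add to them.

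**The case against.** The strongest reply is that this is silence in a descriptive analysis. Protocol 8.1.5.1 says that labs and vital signs are analysed descriptively, and SAP 10.3.2.2 rules out tests for shifts. No primary endpoint, power or alpha is affected. Using all observed values also keeps late-emerging effects visible. All of that stands, and it limits how serious the point is. It does not make the rule coherent: the groups are as treated and data are censored at a switch, so this is not an all-observed, as-randomized analysis. For adverse events the SAP puts the unrestricted version in a sensitivity analysis. For short-term labs it is the only version.

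A reader might go further than the documents allow in several ways:

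- **That the SAP declares these values on-treatment.** It does not. They enter because no rule excludes them.
- **That adverse events beyond 30/70 days are never reported.** They are, in the sensitivity summaries of SAP 10.2.1.1 and 10.2.1.2.
- **That recovery hides abnormalities throughout.** It cannot do so in PCS, liver or maximum-category tables. For lipids and CPK, recovery after a lab-driven stop is also a weak mechanism: Protocol Table 7 has no lipid stopping rule and lets subjects with asymptomatic CPK elevation continue.
- **That the 30-day follow-up labs add much.** They fall at about the upadacitinib/placebo limit and would mostly be kept.
- **That all long-term lab summaries share the gap.** Only the by-visit mean changes do.

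**Conclusion.** The gap is real. Followed as written, the plan puts off-drug labs and vital signs, some of them under other therapy, into the as-treated group that the subject left. The main lab tables and the main treatment-emergent tables then cover different periods after last dose.

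The size is unknown and probably modest. Under full reversal, with 2–10% of assessed subjects off drug, a by-visit mean change shrinks by at most 2–10%. Both inputs are assumptions. It would be tempting to read the 10% planning dropout as the off-drug share, but dropouts who leave the study contribute no labs, some subjects stop late, and reversal may be partial. The number of added PCS or liver cases cannot be estimated from the documents. The two effects need not point the same way, so no net direction of bias is shown.

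The point merits a correction to the SAP because the analysis rule itself is inconsistent. It does not threaten the efficacy conclusions.

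**What to change.** In SAP 10.1.1, 10.1.2, 10.3.2 and 10.4.2, restrict the main lab and vital-sign summaries to values collected before any switch of study drug and within the SAP 10.2 limit: 30 days after last dose for upadacitinib and placebo, 70 for adalimumab. In the by-visit mean changes of SAP 10.3.3.1 and 10.4.3, which follow subjects across a switch by design, apply the same limit from the last dose of the drug being taken when dosing stopped. Keep an all-observed version as a sensitivity table or listing, as SAP 10.2.1.1 already does for adverse events.

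The long-term PCS and liver summaries (SAP 10.3.3.2, 10.3.3.3 and the PCS part of 10.4.3) need no change.

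The cost is about one sentence of SAP text and one programming flag, with no new data and slightly fewer observations per visit. The change removes only the part of the dilution beyond 30 or 70 days. In the Day 29 example, one of six off-drug visits stays in for upadacitinib or placebo, and three of six for adalimumab.
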